After completing the Escalation Part 1 and based on the safety results, we will initiate an expanded cohort, Expansion Part 2 including a total of 19 patients with advanced metastatic CCRCC, to be treated with SLM 4000 in combination with axitinib 5 mg PO BID.

Up to 20 patients in the Expansion Part 2 and pilot phase will have mandatory biopsies at baseline before the start of SLM that will be repeated around day 14 (+/- 3 days) after starting SLM, at Cycle 3 (8 weeks +/- 3 days after first dose of SLM plus Axitinib) and preferably at disease progression, preferably from the same site of the previous biopsy, to study the expression of HIF-a and VEGF by immunohistochemistry (IHC), along with other biomarkers detailed in the correlative studies, before and after treatment with SLM. These tissues will be flash frozen and stored at -80 C to be processed later all at once for the proposed biomarkers.

The candidate patients for the biopsies will be chosen carefully by the treating oncologist and after discussion with the interventional/ body radiologist. Decision will be based on safety, ease of accessibility, tumor size and feasibility of getting the biopsy which can be done either on the primary renal tumor or metastatic site. Patient has to agree to get the biopsies, and sign consent form, after discussing the risks and benefits of the procedure with the provider.

All patients will have a peripheral blood draw at baseline before the start of SLM and repeated on day 14 after starting treatment. This blood will be stored and may be used later to study the protein expression of HIF1a, HIF2a, VEGF and level of SLM.

For Escalation Subjects: All patients will have a peripheral blood draw at baseline before the start of SLM and repeated on day 14 after starting treatment.

For Expansion Subjects: the peripheral blood draw will occur pre-dose and 2 hours post dosing on day 1 then 2 hours post dosing on Day 14 and at Cycles 2, 3, 4, 7, 10 and 13.

Pilot Phase: BSA based dosing. See additional details in protocol Section 14.4.

5.2

STUDY AGENT ADMINISTRATION

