14.5 TREATMENT RANDOMIZATION AND BLINDING

There is no randomization for this study.

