21.2 CT PROTOCOL

The same CT scan protocol will be obtained at 3 time points;

- Visit 1: baseline prior to treatment
- Visit 2: 14 ± 2 days following start of SLM
- Visit 3: 56 ± 3 days following start of chemotherapy (axitinib)

If for any reason baseline DECT could not be performed, we will utilize only regular CT scan subsequently in that setting (cancel further DECT) and there will NOT be a need for day 14 scan. This need to be discussed by PI before enrollment on study.

21.3 DUAL ENERGY CT:

- Contrast: 50% saline mixed with 50% 370mg/ml Iopamidol delivered at 4ml/s (4ml/s (35 s+ 5s) = 160ml of which 80ml is contrast) with delay of 35s (for chest) and 70s (for abdomen/pelvis)
- Positioning: Cranialcaudal acquisition with scan coverage (DFOV) from pubic symphysis to apex of lungs (DFOV to match prior visit). Acquisition at coached total lung capacity (TLC) (recorded for DECT)
- Acquisition: CHEST: The spiral DECT contrast scan with dose modulation with tube A: 120 ref mAs/80kV, tube B: 67 ref mAs/Sn150 kV, with a pitch of 0.55 and rotation time of 0.25sec. The CTDIvol is assumed to be 4.28mGy, with total DLP of 143.2mGy*cm for a 30cm scan.
- Acquisition: ABDOMEN: The spiral dual energy contrast abdomen/pelvis scan protocol uses dose modulation with tube A: 190 ref mAs/100kV, tube B: 95 ref mAs/Sn150 kV, with a pitch of 0.55 and rotation time of 0.25sec. The CTDIvol is assumed to be 10.41mGy, with total DLP of 553.7mGy*cm for a 50cm scan.
- Reconstruction: R1: 0.75 x0.5; R2: 2.0 x 1.4, Qr40(Admire 5), FOV to match prior visits, Energy Series: A, B and M. Keep Raw data.

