21.4 ANALYSIS

- Hypothesis: SLM will improve vascularization of tumors (ie increase in tumor iodine density at visit 2) which will allow for more effective chemotherapy treatment (ie decrease in tumor iodine density at visit 3, and decrease in tumor size). Secondary analysis may examine if baseline (visit 1) levels correlate with SLM response and/or treatment outcome (ie tumors with poor vascularization at visit 1, benefit more from SLM).

- Syngo via (initial analysis on 2.0x 1.4 recon) to produce virtual non-contrast image (VNC), mono energetic 40keV, Iodine concentration PBV (HU and mg/ml)
- Examine analysis results using fixed region of interest (ROI) in tumor volume vs semi-automatic tumor segmentation.

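### If the dual-energy CT 'SLM response' is the iodine change from visit 1, correlating it with visit 1 gives a spurious negative correlation in the hoped-for direction

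*Combined protocol and SAP*

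**What the plan says.** Section 21.4 sets out the imaging hypothesis. SLM alone should produce an "increase in tumor iodine density at visit 2", and the later combination with axitinib should produce a "decrease in tumor iodine density at visit 3, and decrease in tumor size". It then adds: "Secondary analysis may examine if baseline (visit 1) levels correlate with SLM response and/or treatment outcome". The example it gives is "tumors with poor vascularization at visit 1, benefit more from SLM".

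Section 21.2 schedules three scans: one before treatment ("Visit 1: baseline prior to treatment"), one about day 14 of SLM, and one about day 56 after the start of axitinib. If the baseline dual-energy scan cannot be done, the later dual-energy scans are cancelled and the day 14 scan is not needed.

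Neither SLM response nor treatment outcome is defined for this analysis. No statistic, test or unit of analysis is given, and Section 14 contains no dual-energy CT analysis. On a control group, Section 14.5 says: "There is no randomization for this study".

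**The concern.** Write V1, V2 and V3 for iodine density at the three visits. An increase at visit 2 can be measured only against visit 1, the sole earlier scan. Section 21.2 fits this, because it treats the day 14 scan as unnecessary without a baseline. The natural reading of SLM response is therefore V2-V1, and the proposed analysis becomes a correlation of V1 with V2-V1.

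A tumor whose V1 happens to read low will tend to show a larger rise, and one that reads high a smaller rise, whatever SLM does. This is regression to the mean, and its sign matches the example given in 21.4. The design cannot separate it from a real effect: there is no replicate baseline scan from which to estimate measurement error, and no untreated group.

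At stake is an apparent baseline predictor of SLM response, in a trial that Section 14.4 describes as generating hypotheses for a larger one.

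**Working it through.** **Inputs from the documents.** One baseline scan (21.2). Expansion part: "Expansion Part 2 including a total of 19 patients with advanced metastatic CCRCC" (5.1). Pilot phase: 10 patients (Schema). So n is at most 19, or 19 + 10 = 29. These are upper limits: dual-energy CT requires eGFR above 45 (21.6), whereas eligibility admits creatinine clearance above 15 (3.1). The plan states no sample size, reliability, alpha or correlation for this analysis, so there is no figure to reproduce.

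**Assumption.** Test-retest correlation rho of iodine density between 0.5 and 0.95.

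**Expected correlation under the null.** Let V1 and V2 both have variance s², with covariance rho·s². SLM has no effect, or shifts every patient equally.

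- Cov(V1, V2-V1) = rho·s² - s² = -(1-rho)·s²
- Var(V2-V1) = 2(1-rho)·s²
- Corr(V1, V2-V1) = -(1-rho)/sqrt(2(1-rho)) = -sqrt((1-rho)/2)

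For example, rho = 0.9 gives -sqrt(0.05) = -0.22.

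**False-positive rate.** Pearson correlation, nominal two-sided 5%, at least 20,000 simulated trials per cell, no true dependence on baseline:

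| rho (assumed) | null correlation | n = 10 | n = 19 | n = 29 |
|---|---|---|---|---|
| 0.95 | -0.16 | 7% | 10% | 13% |
| 0.9 | -0.22 | 9% | 15% | 22% |
| 0.8 | -0.32 | 14% | 27% | 39% |
| 0.7 | -0.39 | 20% | 38% | 56% |
| 0.5 | -0.50 | 33% | 61-62% | 81% |

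Nearly all of these errors are negative correlations, the hypothesized direction. At rho = 0.9 and n = 19, for instance, 14.7 of the 15.0 percentage points lie in that tail, where 2.5 are nominal.

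**Other outcomes, same simulation.**

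- V1 against an outcome that does not contain V1 iodine, such as change in tumor size: null correlation 0, error about 5%.
- V1 against V3-V2: null correlation 0, error about 5%.
- V1 against V3-V1: the same negative correlation (-0.16 to -0.50). Benefit at visit 3 is a decrease, so the artefact favors highly vascular tumors, against the hypothesis.

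**Oldham's method** correlates V2-V1 with (V1+V2)/2 and is equivalent to the Pitman-Morgan comparison of variances. The covariance is (Var V2 - Var V1)/2, which is zero when the variances are equal. Simulated rejection was then 4.5% to 5.4% in every cell.

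If SLM effects vary between patients independently of baseline, with variance t², the covariance becomes t²/2, which is positive. Take an assumed effect SD of 0.71 baseline SDs, so t² = 0.50·s², with rho = 0.9 and n = 19. Oldham then rejects in 22% to 23% of trials, against 8% for the raw correlation. Almost all of the Oldham errors are positive, and its error in the negative direction stays at or below about 2.5%. With rho = 0.5 and an effect SD of 0.5, the order reverses: raw about 50%, Oldham 8%.

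**Slope correction.** With equal variances and no dependence on baseline, the slope of V2 on V1 is rho. Dividing the observed slope by an assumed rho and subtracting 1 estimates the slope of the change on true baseline, which is 0 under the null. Effects that vary independently of baseline leave Cov(V1, V2) unchanged and so do not disturb it.

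**The case against.** The strongest reply is that the plan never commits to this calculation. Section 21.4 says only that a secondary analysis may be done. It names no response variable, test or alpha, so any false-positive rate belongs to a test that the documents do not specify. That stands as a limit on the claim: V2-V1 is inferred. The inference is strong, however, because no other SLM effect on the scan is described and Section 21.2 makes the day 14 scan depend on the baseline scan.

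The reply also holds against several wider readings.

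- A reader might infer that the whole sentence in 21.4 is compromised. It is not: tumor size and progression-free survival are not built from V1 iodine.
- A reader might take the visit 3 decrease as further false support. Measured from visit 2 it is not coupled to V1; measured from visit 1 the artefact runs the other way.
- A reader might infer that up to three RECIST target lesions per patient will be analyzed as independent. Section 12.2.2 sets that limit for response assessment, and 21.4 does not say that those lesions are the imaging unit.
- A reader might infer that the result will drive patient selection in a later trial. No passage says so.

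Finally, Oldham's method is not a complete cure. It is least reliable when SLM effects differ between patients, which is the situation this analysis would explore.

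**Conclusion.** The concern holds for one reading of one optional analysis: V1 against V2-V1, the natural reading of SLM response. There the raw correlation is biased toward the stated example. The size depends on reliability, which the documents do not give. It is modest if rho is about 0.95 (two-sided error about 10% at n = 19) and severe if rho is about 0.5 (about 62% at n = 19, 81% at n = 29). These rates assume equal variances at the two visits and no baseline-dependent effect. Independent variation in SLM effects lowers the raw method's error, for example from 15% to 8% at rho = 0.9 and n = 19 with an effect SD of 0.71.

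The documents do not support saying that the plan will report a false predictor, only that the risk is raised and unguarded. No primary endpoint, sample size or dosing rule depends on it. It is worth correcting because the bias favors the hypothesis and the correction costs little.

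**What to change.** In Section 21.4:

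1. Define SLM response as V2-V1, define treatment outcome, and state that SLM response will not be tested by its raw correlation with V1.
2. Relate V1 iodine to outcomes that do not contain it, such as percent change in the target-lesion sum or progression-free survival.
3. If baseline dependence of the iodine change is examined, use Oldham's method (or Pitman-Morgan). Read only a negative correlation as support. State that the method assumes equal variances apart from any baseline dependence, and that SLM effects varying independently of baseline produce a false positive correlation. Alternatively, report the slope on V1 corrected over a stated range of measurement error.
4. Use one value per patient, or a patient random effect if several lesions are analyzed.
5. Label the result hypothesis-generating.

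The cost is a few sentences and a little more analysis work, with no new scans. The reported correlation will probably be smaller, and Oldham's method loses some power when SLM effects vary between patients.

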21.5 COST

DECT data acquisition: 1hr scan charge (\$470), supplies for injector etc (\$25), contrast (\$25), radiology read (\$100) = \$620 x 3 visits = \$1,860 per subject

Analysis: [name] grad RA, \$25 x 4hr per case = \$100

21.6 CRITERIA

- Tested and checked by HCCC nurse prior to each imaging study visit
 - Subject must have eGFR>45
 - Negative pregnancy test (women of child bearing age)
 - Schedule clinician available for attendance in CT facility during contrast administration

21.8 SUPPORTIVE STUDIES ON WHICH THE PROTOCOL IS BUILT

Abdominal contrast timing (15-20s: early arterial, 35-40s: late arterial, 70-80s: late portal, 100s: nephrogenic phase).

From mRCC treatment response DECT published study (Hellbach et al. 2017):

- 1.3 ml/kg body weight 350mg/ml iomeprol at 2.5ml/s (~80ml contrast for 60kg adult) with delay of 70-80s (late portal phase for abdomen)
- Crainalcaudal from pubic symphysis to apex of lungs at TLC
- DECT protocol on Siemens 128-slice with dose modulation (ref mAs not provided) tube A: 100kV, tube B: 80kV with pitch of 0.6 and rotation time of 0.5s

From NSCLC treatment response DECT published study (Baxa et al. 2016):

- 80mL 250mg/ml iomeprol at 4ml/s with 60ml saline flush (140ml of which 80ml contrast) at arterial bolus trigger (early arterial for abdomen) and bolus trigger +20s (late arterial phase for abdomen)
- DECT protocol on Siemens Flash with dose modulation tube A: 160 ref mAs/80kV, tube B: 68 ref mAs/Sn 140kV, pitch of 0.9 and rotation time of 0.33s. with average DLP of 149.6mGy*cm

From MESAs study (current [name] study):

- 50% saline with 50% 370mg/ml Iopamidol at 4ml/s (4ml (17s+5s) = 96ml of which 48ml is contrast) with delay of 17s (early arterial phase for abdomen)
- Caudocranial at FRC
- DECT protocol on Siemens Force with dose modulation tube A: 210 ref mAs/80kV, tube B: 117 ref mAs/Sn150 kV, with a pitch of 0.55 and rotation time of 0.25sec. The CTDIvol is assumed to be 7.27mGy, with total DLP of 430mGy*cm for a 30cm scan.

From Smoking cessation (current [name] study):

- 50% saline with 50% 370mg/ml Iopamidol at 4ml/s with delay of 17s (early arterial phase - abdomen)
- Caudocranial at FRC
- The spiral DECT contrast scan protocol uses dose modulation with tube A: 120 ref mAs/80kV, tube B: 67 ref mAs/Sn150 kV, with a pitch of 0.55 and rotation time of 0.25sec. The CTDIvol is assumed to be 4.28mGy, with total DLP of 143.2mGy*cm for a 30cm scan.

